10.4 Main components of the systems

The architecture is organised in two layers: the mechatronic layer and the cognitive layer. The mechatronic layer is organised around a Controller Area Network (CAN) infrastructure and is compounded of a number of nodes used to operate the different mechatronic components. Noteworthy are: 1. the different drivers for the brushless motors on the front and on the rear side of the vehicle (denoted as Back Left Noder, Back Right Node, etc.). Such drivers are "intelligent components" able to implement position, velocity or torque feedback control loops. Directly connected to the drivers is an enable signal coming from the mechanical brakes of the device: whenever the user pulls the handle of the brakes, the disable signal to the driver causes an immediate disconnection of all the motors.

The cognitive layer comprises a number of computing units (boxes) devoted to heavy data processing activities. In particular,

- NUC 1: is a Next Unit of Computing and is used to:
 - \circ detect and interpret the QR landmarks for localisation;
 - manage the RGBD sensor looking at the user used for emotion recognition;
 - execute the reactive (short range) planning algorithms
 - host the software infrastructure used for the web based graphical interface;
- NUC 2: is a Next Unit of Computing and is used to:

- perform gait analysis using the data collected from the RGBS sensor
- detect human target and other walkers in the surroundings.

The two boxes are connected through an high speed switched Ethernet link. The cognitive and the mechatronic layers are connected to each other by an embedded board (a Beaglebone) that acts as gateway. This board can also be used to implement control and estimation tasks requiring a moderate computation load (in particular guidance algorithms and localisation).

[figure not shown]

Figure 2: Diagram of the main electronic and mechanical components

In order to reduce the traffic on the CAN bus, the device also mounts a Bridge CAN bus to filter the messages from and to the drivers on the front motors. Grip and Force sensors are directly connected to the board.

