10.10 Risk analysis

Risk analysis, including the identification of hazards, risks associated with the manufacture (consider those factors related with the selection of the product, materials, software, etc.) and risks related with the actual use of the product along with a description of the actions taken with the aim to minimizing or even eliminating the identified risks.

Risk	Mitigation Action	Severity	Likelihood to Happen	Detectability	Risk #
The FriWalk moves out of control running over the user or by- standers	Presence of passive devices to switch off the machine (lanyard, switches)	7	2	2	28
The user dresses or shoelaces catch on the mechanical mechanisms of the front or rear motors causing a fall	Plexiglass cover on mechanical parts	5	1	2	10
Electrical shock	Internal Cabling. Insulation of the batteries.	3	2	3	18
Injuries caused by tips, sharp edges, or hot surfaces	High quality of the frame. Rounded edges for the carters.	2	2	2	8

Leakage of corrosive fluids from the batteries	Triple mechanical barrier between the batteries and the environment.	8	1	5	40
Explosion or meltdown of the lithium batteries	State of the art protection mechanisms in the devices. Extensive testing.	8	0.5	5	20

The different risks are listed in the following UNE-14971 compliant table and described in detail in the text below. In the table Severity, Likelihood and Detectability are numbers chosen in the range 0 (non existent) - 10 (critical).

Risk 1: the FriWalk moves out of control running over the user or by-standers

Since the FriWalk is capable of autonomous motion, one of the main risk that is potentially harmful for the user is related to a severe software failure, which could make the robot move unpredictably. The FriWalk could in this case on its own alone, running over the user or causing her/him to lose her/his balance. Similarly, the robot could crash against other patients or bystanders or cause material damage. In order to minimize/eliminate the identified risk, to preserve user safety, we installed two devices:

- a safety lanyard which connects the user's chest with the robot. If the distance between the user and the robot exceeds the lanyard length, than the power supply is immediately and automatically detached;
- a safety switch mounted in the two bars of the seat. In this way, if the FriWalk goes backwards, as soon as the seat comes into contact with the user legs the power supply is immediately and automatically disconnected.

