We point out that both mechanisms operate directly on the power switches; therefore they do not need any software signal to be activated.

Finally, the use of correct-by-construction programming mechanisms, of well tested versions of the Linux Kernel and of well known computing devices (adopted and supported by a large community) mitigates the risk of a severe software failure.

Risk 2: the user dresses or shoelaces catch on the mechanical mechanisms of the front or rear motors causing a fall

The tyres are connected with the motors by means of a gear system on the rear and a pulley–belt system on the front. In order to minimize the risk of entanglement (but also of small injuries, bruises or bunts), all the moving parts (like gears, pulley and belts) have been covered with a thick plexiglass case so that the user cannot come in direct contact with them.

Risk 3: Electrical shock

Regarding the electrical risk, since there are lead battery inside the box (which could electrocute the user in case of shortcuts), we designed an insulation system to avoid direct contacts of batteries with the walker frame. Moreover, all the wires are cabled

inside the walker frame in order to minimize the possibility of direct contact with the user's body. The electrical circuits respects the requirement of the current regulations (in particular as regards the adoption of high quality connectors).

Risk 4: Injuries caused by tips, sharp edges, or hot surfaces

The walker is a derivative of the a high quality commercial walker, which is carefully designed and manufactured to avoid injuries and accidents of the kind. The additional components are packed within plexiglass cases or aluminium boxes. All the edges are rounded and the gap between the hot part (motors) inside the case are sufficient to avoid contacts with hot parts.

Risk 5: Leakage of corrosive fluids from the batteries

The lead batteries are protected by a pair of fuses to prevent short circuits that could determine overheating and meltdown of the lead batteries. Besides, the batteries we selected are based on a acid lead gel (which does not easily leak out) and are endowed with a thick plastic cover that contains the lead core. Finally, a third barrier is the aluminium box that contains the batteries.

Risk 6: explosion or meltdown of the lithium batteries

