10.16 Circuitry diagrams

FriWalk is equipped with an electrical circuit made of three circuits, dedicated to the management of the power supply of all mechatronic and electronic components, included the batteries. This circuit is basically made of three sections, which are connected together:

- charging circuit: responsible of the charging of the lead batteries;
- sensing circuit: which checks the correct operation of the power supply circuit and collects inputs from the user;
- power supply circuit: activates and deactivates the supply to all system components.

All these circuits are under the control of an ST, which is a microcontroller interfaced with a development board. Moreover, all these circuits, because of encumbrance, are splitted over three boards mounted one over each other:

- relay board;
- charging board;
- sensing and microcontroller board.

10.16.1Relay board

The schematic circuit of the *relay board* is reported in Figure 16. This board activates the relay according to the instruction coming from the microcontroller. As soon as the microcontroller sends the information to excitate a relay coil, the corresponding output is activated, turning on the desired mechatronic component.

This circuit is responsible of the motors and of the logic power supply. Moreover it hosts a reed relay, which is a component attached to a lanyard emergency strip, so that, as soon as the strip is pulled, an information is sent to the microcontroller, which switches off the power system, but preserves the logic section. The reason of such a choice is due to let the user know if the strip has been pulled, so that the graphical user interface has to interact directly with the user in this emergency situation. At the same time, the motors have to be switched off.

[figure not shown]

Figure 16: Relay board schematic circuit

The *relay board* derived from the electrical circuit reported in Figure 16 is reported in Figure 17.

[figure not shown]

Figure 17: Relay board

10.16.2Charging board

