The schematic circuit of the *charging board* is reported in Figure 18. This section of the circuit provides the power from the two lead batteries. During charging phase, the battery are connected in parallel, in order that they can be recharged independently (12V DC). During the common phase, the battery are connected in series, in order that they supply the correct desired voltage (24V DC). As soon as one both the two charger (CH1 and CH2) is connected to the box, that the circuit automatically switches from the series configuration to the parallel configuration thanks to one relay.

[figure not shown]

Figure 18: Charging board schematic circuit

The *charging board* derived from the electrical circuit reported in Figure 18 is reported in Figure 19.

[figure not shown]

Figure 19: Charging board

10.16.3Sensing and microcontroller board

The schematic circuit of the *sensing board* is reported in Figure 20. This board hosts the microcontroller, which is the brain of the power supply of all components and manages the inputs coming from the user. This circuit is equipped also with 5 leds, which gives direct information about the status of the different mechatronic components.

[figure not shown]

Figure 20: Sensing and microcontroller schematic circuit

The *sensing and microcontroller board* derived from the electrical circuit reported in Figure 20 is reported in Figure 21.

[figure not shown]

Figure 21: Sensing and microcontroller board

[figure not shown]

Figure 21: Outline for the HW/SW architecture

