An example subscriber is the localisation module, which subscribes to the encoder readings, to the IMU and to the landmark readings. The module implements an Extended Kalman Filter (EKF) [3] which fuses these different layers of information together to produce a localisation accuracy within tens of centimetres. Such data is propagated on to the zeroMQ bus; therefore the localisation module is both a consumer and a producer. The picture reflects the current implementation, in which the localisation module is deployed inside the gateway. However, the use of the middleware allows us to relocate the module to any of the computing nodes (e.g., NUC1 or NUC2) if required by the application.

The safety devices (safety lanyard, and safety bar to prevent the system from running backward over the user) are connected to a microcontroller. When an emergency situation occurs (lanyard stripped off, or safety bar pushed), the motors are immediately powered off. Moreover, a digital signal is generated for the gateway. The Walker Hardware Manager sends a shutdown messages to the NUCs through the zeroMQ bus. As soon as an ack is received, the gateway is powered off.

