Technicians have access to a number of configuration parameters for the walker and they can easily perform diagnostic activity (e.g., to see if the different devices are working properly, if the localisation produces correct results, etc). Such data are extremely useful during the development of the different features of the walker and during its maintenance.

10.21.4Software Quality Control

Quality control for the software is enforced in five different ways:

- 1. The most important modules written in C++ (i.e., the Guidance Control, and the Activity Execution) are written using the metaprogramming approach described in Section 11.4.2. This technology allows us to solve many of the possible programming error during the compilation phase;
- 2. Unit testing: each delivered software component comes along with a number of test cases to identify the most common sources of bugs;
- 3. Integration Testing: all the operation scenarios have been extensively tested in realistic conditions, simulating a range of possible problems;
- 4. fault injection: some of the most dangerous scenarios in which one of the components goes offline (e.g., due to a power failure or to a battery exhaustion) have been simulated by turning off the component. This is possible because a software controlled relay is used to power up all the hardware units, thus enabling a selective power down of the the different computers. As a result of these checks, we have implemented a whole range of periodic diagnostic monitoring activity, such as an heart-beat signal exchanges between the different units to figure out that they are alive.
- 5. logging mode: each component of the control logic can be set to operated in logging mode and produce a number of logs that can be analysed post-mortem in case of run-time problems that were not discovered during the testing phase.

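### The software independence that 10.10 claims for the Risk 1 cut-offs is not supported: 10.16.1 routes the lanyard through the power microcontroller, and 10.19 connects the seat bar to a microcontroller too

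*Protocol*

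**What the plan says.** Section 10.10 describes Risk 1 as the walker moving unpredictably because of a severe software failure. The mitigation cell in the risk table begins "Presence of passive devices to switch off the machine (lanyard, switches". The text below the table describes two devices: a lanyard that detaches the power supply when the user and robot separate beyond its length, and a switch on the seat bars that does the same when the walker backs into the user's legs. It then states that "both mechanisms operate directly on the power switches; therefore they do not need any software signal to be activated".

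The circuit description reads differently. Section 10.16.1 says of the lanyard strip that "as soon as the strip is pulled, an information is sent to the microcontroller, which switches off the power system", with the logic section kept alive. On the relay board it says: "This board activates the relay according to the instruction coming from the microcontroller". Section 10.16.3 says of the sensing board: "This board hosts the microcontroller, which is the brain of the power supply of all components".

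Section 10.19 covers both devices: "The safety devices (safety lanyard, and safety bar to prevent the system from running backward over the user) are connected to a microcontroller". It adds that triggering either one powers off the motors at once, and that a separate signal also goes to the gateway.

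**The concern.** The mitigation is credited with a specific property: it works whatever the software is doing. That property matters because the hazard is a software failure. If the lanyard acts only by informing a programmable controller, which then opens the relays, the property does not hold as stated, and the risk table describes as passive something that is not.

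The stake is participant safety, not any statistical result. Participants are 75 or older, and one of the two clinical settings enrols patients shortly after hip-fracture surgery. The walker has motors capable of autonomous motion. Section 10.11 reports that no preclinical trials have been done on it, and section 5 says the annex went to the national device regulator. Readers of the risk table are therefore relying on this sentence.

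**Working it through.** No sample-size or error-rate arithmetic applies. The check sets the sections side by side and asks which failures separate them.

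**1. Lanyard.** Section 10.10 has the lanyard acting on the power switches with no software signal. Section 10.16.1 has it sending information to the microcontroller, which does the switching through relays driven on its instruction. Section 10.16.3 agrees with the second account. The two cannot both describe the same lanyard.

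**2. Seat bar.** Section 10.10 states a direct path for this device as well. Section 10.19 says it is connected to a microcontroller and that the motors lose power immediately, without naming the element that cuts the supply. A contact could be wired both to the supply and to a controller input, so this is a poor fit and not a contradiction. The relay-board text in 10.16.1 describes only the lanyard.

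**3. Which failures tell the two accounts apart.** I take the controller in 10.19 to be the power microcontroller of 10.16; the text does not say so.

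| Failure | Lanyard if 10.10 is right | Lanyard if 10.16.1 is right |
|---|---|---|
| Onboard computers or gateway misbehave, power microcontroller healthy | Cuts power | Probably cuts power |
| Power microcontroller dead or in reset | Cuts power | Relays probably released, so motors already off |
| Power microcontroller hung with relay outputs held on | Cuts power | Does not cut power |

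The second row rests on 10.16.1, where an output becomes active when the microcontroller energises the relay coil. Losing that drive would then probably remove motor power. The reset-state wiring itself is not given.

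**4. Standing of Risk 1.** Severity × likelihood × detectability = 7 × 2 × 2 = 28, as printed. The six scores in that table are 28, 10, 18, 8, 40 and 20, so Risk 1 ranks second. The table gives no acceptance threshold and does not say whether scores are before or after mitigation, so no corrected score can be derived.

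**5. Existing test evidence.** The fault injection in 10.21.4 simulated components going offline by turning them off. It does not report triggering the lanyard or seat bar while the power microcontroller was hung.

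**The case against.** The strongest reply is that the power microcontroller is not the software Risk 1 has in mind. The same discussion goes on to the Linux kernel and the computing devices, and motion commands come from guidance control through the gateway. In 10.19 the gateway signal is additional to the motor cut-off, so the cut does not wait for that layer. Harm would need two faults together: runaway motion software and a power controller stuck on. This stands and limits the size of the point. It does not reconcile the wording of 10.10 with that of 10.16.1.

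The schematics in Figures 16 and 20 are not shown here and could settle the matter. That also stands, so no wiring fault is asserted.

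The remark in 10.21.4 that "a software controlled relay is used to power up all the hardware units" looks like further support. It is weak, because it explains how computers were selectively powered down in testing and does not describe the emergency motor cut-off.

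The brake handle is a separate protection: "whenever the user pulls the handle of the brakes, the disable signal to the driver causes an immediate disconnection of all the motors". It helps, but the user must pull it, so it does not replace an automatic device.

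A reader might infer that the gait-speed test, where the robot follows behind the patient, is where the gap bites. The documents do not support this. The lanyard trips on separation and the seat switch on backward motion; neither is described as tripping on forward motion into the user, however it is wired. The text also does not say that the lanyard is worn in that test.

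**Conclusion.** The claim of software independence in 10.10 is contradicted for the lanyard and doubtful for the seat bar. It is an inconsistency in the device annex about a stated safety property of the main protection against runaway motion, and it should be resolved before participants use the walker.

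Two stronger readings go too far. One is that any software failure would disable the lanyard: faults in the onboard computers or gateway would probably still be stopped, and a dead or reset microcontroller would probably fail safe. The other is that the walker is wired unsafely: the text conflicts with itself, and without the schematics nobody can tell from this copy which account is true. What remains is the case of a microcontroller hung with its relay outputs on, for which the protection claimed in 10.10 is not supported as written. This assumes that 10.16.1 describes the device as built and that energised coils mean motor power on.

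**What to change.** 1. Before first participant use at any site, bench-test each FriWalk with the power microcontroller's firmware halted and the motor-relay output held energised. Do not hold the controller in reset: that would probably drop motor power before anything is triggered and falsely confirm 10.10. Confirm that the motors are powered, then trigger the lanyard and the seat bar separately and record for each whether motor power drops.
2. If it drops, keep the statement in 10.10, and correct 10.16.1 and 10.19 to show the direct path.
3. If it does not drop for a device, choose one of two routes. Either wire that contact in series with the motor supply or relay coil and retest, or correct the risk table and text in 10.10 to say that the cut-off depends on the power microcontroller, and reassess the Risk 1 score.

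Section 10.22 already requires hardware and software integration tests, so this check can be added there by name. The cost is a short bench test per device, a few corrected sentences and possibly a brief delay to first use. Rewiring is needed only if the test fails and the sponsor wishes to keep the claim.

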10.11 Summary of preclinical trial

Summary and analysis of any preclinical trial carried out (including experimental data), in-cluding the results, mechanical trials, electrical trials, software validation, safety trials and any other relevant trial. In this point it is necessary to indicate those technical standards or internal manufacturer procedures that have been followed.

However, preliminary tests have been conducted on a low fi prototype derived from DALi's cWalker with the medical staff with the purpose of identifying requirements Preclinical trials have not been conducted on the FriWalk as yet.

However, preliminary tests have been conducted on a low-fi prototype derived from DALi's cWalker with the medical staff with the purpose of identifying requirements and define application scenarios. Many of the design choices reported about above derive from this experience.

More in detail, the experience with the user collected with the low-fi prototype have been translated into design guidelines concerning a number of different points. The most important are listed next.

Guideline n. 1: selection of the device platform

For the DALi project, the device was developed with a clear goal in mind: demonstrate that the solutions could be viable using low cost hardware solution. This philosophy lead

us to the adoption of a very low cost mechanical platform (one that is possible to buy for less than 150 Euros). While the goals of the DALi project have been met, we encountered the following problems: 1. The platform did not lend itself to the easy integration of mechatronic devices and of the cabling, 2. The presence of mechanical backlashes significantly exacerbated the difficulty of implementing guidance algorithms, 3. The stigma deriving from using a bad looking device could potentially discourage its use in public spaces.

For these reasons, we have decided to *improve the quality of the platform* because the benefit could be worth the price, and elected the TRIONIC platform mentioned above.

Guideline n. 2: electrical design

Among the problems encountered with the use of DALi device, there were occasional disconnections of the cables, shunts (which several times caused components failure) and electric shocks. Such problems determined frequent slow-down in the experimental work agenda and were a constant cause for concerns when we involved older adults in the user validation.

In view of these experience, we decided to use the *maximum care in the quality of the connector, in the cabling and in the insulation of the batteries*.

Guideline n. 3: replacing brakes with motors

DALi's cWalker had a couple of electromagnetic brakes applied on the rear wheels instead of the motors. This choice was determined by the following considerations: 1. The cost and the complexity of the control electronic for a brake is way lower than the one required by a motor, 2. Having a passive device (i.e., a device incapable of autonomous motion) is arguably safer than having an active device.

The changed context of the ACANTO project forced us to consider other requirements such as the ability of the walker to follow the user for the SPBB test. What is more, we have developed a control approach named "simulated passivity" in which the rear motors can be actuated to steer the vehicle without any apparent change in the forward velocity (which could endanger the user). On the other hand, the combination of gearbox and brushless motors produces, when required, a behaviour very similar to a braking action.

With these considerations in mind, we decided *that the use of rear motors instead of brakes had a clear potential to improve the flexibility of the device without sacrificing safety.*

Guideline n. 4: adoption of a structured testing procedure for software

In the DALi project the integration of the different components was carried out in the very last months of the project. The foreseeable result was an evident lack of robustness in the behaviour of the product, which generated frequent bugs very hard to identify causing delays in the project.

This experience spurred us into the *adoption of a formalised testing procedure*, in which each component is first tested in isolation and only after this test is passed is the integration completed and the system tested as a whole.

This policy, in combination with the development of a well-founded software architecture, has lead us to a drastic reduction in the number of bugs encountered during the "user validation" phase. The integration testing phase is currently under way for all the clinical applications.

Guideline n. 5: Design of robust software architecture

In a complex project like ACANTO, one of the critical and potentially most error prone activity is the integration of the different components (which come from different research groups). As observed in Section 7.4, in the DALi project this activity gave rise to frequent problems (i.e., bugs very difficult to identify).

In order to alleviate the problem, we have designed a very robust software architecture based on the widespread adoption of the zeroMQ middleware and of the template metaprogramming paradigm, which drastically reduces the probability of "trivial" programming errors detecting them during the compilation phase of the application.

7.6 Guideline n. 6: Test the applications with PhD students and intact users before moving to the validation with actual users.

Our experience with DALi revealed that the validation with realistic users (i.e., older adults with degrading abilities) could be quite demanding both from the physical and from the psychological point of view. For this reason, our current ethical guidelines require that for any experimentation activity that the *very same protocol that will be used for older adults is first administered to a good number of younger and physically intact users* (e.g., PhD students and technical stuff). The level of physical and psychological test is tentatively evaluated during this phase to fine tune such parameters as the duration of the exercise or the number of repetitions.

